Appendix I: ECOG Performance Status

Appendix II: Patient Information Sheet and FACT-Lym

Appendix III: Lymphoma Blood Collection Kit – Specimen Checklist and Shipping Instructions

Appendix IV: Percent Bone Marrow in the Adult Skeleton

Schema

PD at any time
Subsequent treatment for lymphoma
Patient refusal
Failure to return for evaluation
during observation

→ Event Monitoring

1. Cycle length = 3 months for Cycle 1 (assessment at 3 months)
2. Cycle length = 3 months for Cycles 2-4 (assessments at 6, 9, and 12 months)
3. Cycle length = 6 months for Cycles 5-8 (assessments at 18, 24, 30, and 36 months)
4. Cycle length = 12 months for Cycles 9-10 (assessments at 48 and 60 months)
5. 10 years after registering no further follow-up is necessary.

Generic name: 90 Yttrium Ibritumomab tiuxetan	Generic name: Rituximab
Brand name: Zevalin®	Brand name: Rituxan®
Lymphoma SPORE abbreviation: Y2B8	Lymphoma SPORE abbreviation: RITUX

1.0 Background

Non-Hodgkin lymphoma (NHL) is the 7th most common cancer in both men and women. Within NHL, follicular lymphoma (FL) is the second most common (diffuse large B-cell lymphoma is the most common). Typical teaching regarding FL incites the usual mantra of “treatable but not curable”. However, a number of studies with very long-term follow-up demonstrate 20% of patients are cured.(1) We acknowledge that in these studies patients were not routinely scanned and biopsied throughout the many years of follow-up; however, the point is that they never manifested obvious recurrence and lived out their life and died without FL. Thus, they were “effectively cured”.

The treatment of FL continues to evolve. For patients with new, untreated FL the standardized approach is to perform a history and physical, obtain basic laboratory tests, staging with a CT or PET/CT and a bone marrow aspiration and biopsy. A treatment plan is then formulated based initially on whether or not the patient requires chemotherapy. The commonly used criteria to start chemotherapy are the GELF criteria (2, 3) or the Follicular Lymphoma International Prognostic Index Score (FLIPI score). Patients who achieve a complete remission (CR) with initial therapy have a better outcome than those who merely achieve a partial remission (PR).(1)

1.1 **Patients who Need Chemotherapy:** Patients who have the need for chemotherapy are typically treated with rituximab/chemotherapy followed by either observation, two years of rituximab maintenance,(4) or a single dose of radioimmunotherapy (RIT).(5, 6) Rituximab and RIT both prolong time to progression (TTP) but their effects on overall survival (compared to observation followed by repeat treatment at time of relapse) are unknown. Bendamustine/rituximab (BR) produces higher overall response rates (ORR) and longer progression-free survival (PFS) with less toxicity than RCHOP.(7) There is currently no overall survival (OS) benefit from BR.

There are many clinical trials being performed for FL patients who meet the criteria for chemotherapy. ECOG 2408 is the current national trial in the cooperative groups. It is BR based with 2 years of rituximab maintenance. One arm contains BR + Velcade and one arm has Revlimid/Rituximab as maintenance. This study is predicted to reach accrual in 2014. It will not interfere with this proposal since patients must meet chemotherapy requirements. There also is an upfront Revlimid/rituximab trial.

1.2 **Patients Not Requiring Chemotherapy:** There is no movement yet to treat these patients with chemotherapy – **thus the main approaches used are observation, rituximab immunotherapy, or RIT.** The hypothesis is that patients with advanced but asymptomatic FL (AFL) are not reliably curable and since they may do well for years to wait for treatment. This approach of treatment nihilism dates back to the pre-rituximab days when the options were chemotherapy vs. observation. Since observation was shown to not reduce survival and since chemotherapy was toxic the choice was much simpler in favor of observation. The advent of immunotherapy and RIT changed the equation in that these treatments were mild, short in duration and effective. Thus, in 2014 *the real key issues in this group of AFL patients are preventing chemotherapy (with its inherent toxicity and risk of myelodysplastic syndrome), preserving QOL, preventing transformation to large cell lymphoma, and aiming to effectively cure a group of patients with initial therapy.*

Why some patients choose observation over rituximab or RIT is not clear. This is likely due in part by patient and physician input. The number of AFL patients in the United States being observed has dropped to about 18% since the institution of rituximab but this figure was derived from all new FL patients.(8) It is clear that ***observation*** remains a recognized standard (*a* standard not necessarily *the* standard) for these patients.

Immunotherapy with ***rituximab*** has eroded support for observation, although to date, no OS benefit exists for early treatment. In this patient population, studies have shown that four doses of rituximab (no maintenance) can produce approximately a 75% ORR with 6 - 33% CR and in some patients a very long time to next chemotherapy (TTNT).(9, 10) Preliminary results from the RESORT ECOG trial in this same patient population showed an ORR of 71% after 4 doses of rituximab with approximately a 15% CR. Scheduled maintenance after induction is not better than rituximab when needed as far as prolonging survival.(11) Ardeshta et al(12) studied 379 patients with AFL by randomizing them between observation versus rituximab induction or rituximab induction followed by maintenance every two months for two years. They subsequently closed the rituximab induction only group beginning a new treatment rather than progression free survival. The primary endpoint was so that it became a two arm study – observation versus rituximab maintenance. There were 84 patients who received rituximab induction alone. 46% of patients in the observation group were still free of treatment at three years compared to 88% in the maintenance rituximab group being free of retreatment at three years. 78% of those in the rituximab induction group retreatment free at three years. Thus, at the three-year mark, rituximab induction only and rituximab maintenance were similar and both were superior to observation as far as preventing treatment at three years. Quality-of-life scores with regard to mental adjustment and coping were improved in those who receive maintenance rituximab. This study supports the use of rituximab monotherapy for patients with AFL. It still does not completely settle the issue of whether these patients should receive rituximab maintenance after rituximab induction. There was no difference in overall survival nor time to transformation. With respect to maintenance rituximab versus rituximab induction without maintenance, again there was no difference in overall survival or histologic transformation or time to start a new therapy. There was however an improvement in progression free survival with rituximab maintenance compared to rituximab induction only.

A second recently reported study by Ibatici et al.(17) treated 50 patients with stage II “bulky” stage III or IV FL with a single treatment course of Zevalin. The median age was 60 years and 14% had elevated LDH. The ORR was 94% and the CR rate was 86% with a median follow-up of 38.8 months. The median PFS has not yet been reached. The three-year estimated PFS was 63% and the 3-year OS was 90%. No cases of secondary hematological malignancies have been observed.

It is important to note that this study included patients who met GELF criteria and those that did not meet GELF criteria. The median PFS and OS for the 19 patients (40%) who fulfilled GELF criteria was 21.9 months and 50 months, respectively. In the other 29 patients who did not meet GELF criteria the median PFS and OS has not yet been reached. The estimated 3-year OS and PFS in patients without GELF criteria were 97% and 75%, respectively. These data support the premise of this study that patients who do not meet GELF criteria should have a very high CR rate and a long TTP. It is also likely that patients with these characteristics you receive rituximab will also do better; therefore, it is still not clear which approach is best.

Ongoing Clinical Studies: It has been felt by many investigators to be impossible to do a randomized study in this AFL patient population; thus, there are no current trials open in the US at this time.

It is been demonstrated that patients with FL who achieve CR have a chance at very long-term survival and likely approximately 20% are effectively cured.(1) Whether FL is “curable” is a contentious subject as discussed above. Because of the long survival of these patients and the development of novel agents it is reasonable to try and take advantage of the discovery of an early stage asymptomatic patient, achieve CR with a non-chemotherapy regimen, and then observe. *Avoiding chemotherapy for ≥ 5 years with a non-toxic, non-chemotherapy regimen would be considered meaningful to patients, physicians, and health care providers.*

1.3 **Hypothesis:** Treatment of patients with asymptomatic FL with Zevalin RIT will produce a higher CR rate than rituximab alone, and a higher % of patients progression-free at 3 and 5 years. The rationale for these parameters is that this treatment is low toxicity, brief, and will produce valuable remission time and effectively cure a percentage of these patients.

An additional important parameter is the time to chemotherapy (TTC). This parameter is important but can be years to measure. Patients who achieve a CR are in turn less likely to need chemotherapy. In addition, if the patient enters CR then transformation is less likely. Indeed, patients treated with rituximab have a lower chance of transformation than those observed;(18) thus supporting the view that less tumor, less chance of transformation.

1.4 **Translational research:**

Beta-2 microglobulin and LDH: this combination of factors has recently been shown to be prognostic in follicular lymphoma.(19) Patients with a normal beta-2 microglobulin had improved response to chemotherapy given with RIT consolidation in that study. We will evaluate this combination as prognostic factors in this prospective trial.

Bcl-2 mutations: Our group ([name], [name], [name], [name]) have recently described the functional and adverse prognosis of FL patients whose tumors have exon 2 bcl-2 mutations ([name] et al submitted for publication). The rate of single nucleotide variants (SNV) was 53% (20/38). This was confirmed in an additional sample of 11 cases where 73% (8/11) also had SNV's. It is unknown what the incidence of these mutations are in AFL patients. We would anticipate that it would perhaps be lower and we postulate that if present, these patients may have a worse prognosis. This trial provides an opportunity to test this hypothesis in a group with lower risk disease.

Serum Cytokine Levels-IL-12: We measured IL-12 levels in patients with follicular lymphoma and found that those patients with higher pretreatment IL 12 (>0.56 ng/mL) had a shorter progression free survival.(20) This will be evaluated in this prospective study.

Tumor microenvironment: Malignant B cells from biopsies of tumors in patients with lymphoma do not play a passive role but instead clearly drive the differentiation and function of intratumoral T cells (**Figure 1** from (21). Malignant B cells have been found to express multiple ligands responsible for inducing regulatory T cells (Treg cells) and suppressing other intratumoral effector cells. Lymphoma B cells have been found to express CD70, and CD70/CD27 signaling promotes the induction of FoxP3- positive Treg cells. (22) Malignant cells also express PD-L1, and interactions with PD1 expressed on intratumoral immune cells results in immune suppression.(23, 24) B cells from lymphoma biopsies have been found to secrete chemokines and cytokines responsible for further immune suppression. CCL22 secreted by lymphoma B cells is involved in chemotaxis and migration of intratumoral Treg cells that express the receptor CCR4, which results in recruitment of Treg cells to the tumor microenvironment.(22) Treg cells recruited to sites of lymphoma have been shown to suppress both effector CD8+ T cells and intratumoral CD4+ cells.(22, 25) Cytokines and chemokines such as IL12 and

CXCL10 produced by the malignant B cells also have a role in regulating effector T-cell function.(20, 26) However, IL-12 has been shown to induce T-cell exhaustion, resulting in ineffective T cells that are unable to proliferate or lyse target B cells.(20) Overall, malignant B cells skew the T-cell balance within lymph nodes promoting Treg cells and inhibiting effector T cells or TH17 cells.(27)

[figure not shown]

Fig 1. Mechanisms whereby malignant B cells modulate the function of intratumoral T cells. CCL22, chemokine (C-C motif) ligand 22; CCR4, chemokine (C-C motif) receptor 4; FoxP3, forkhead fox P3; PD-1, programmed cell death-1; PD-L1, programmed death ligand 1; TIM3 - T-cell immunoglobulin and mucin domain 3; T_{reg} cells, regulatory T cells.

2.0 Goals

2.1 Primary

2.11 Test the hypothesis that a single dose of Zevalin RIT will increase the CR rate over that achieved with standard rituximab in patients with untreated asymptomatic FL.

2.2 Secondary

2.21 Test the hypothesis that Zevalin RIT will improve progression-free survival.

2.22 Test the hypothesis that Zevalin RIT will improve time to next (any) therapy and time to next chemotherapy.

2.3 Correlative Research

2.31 Study the incidence of exon 2 bcl2 mutations in patients with AFL.

2.32 Measure Tregs and tissue monocytes in on-study FL tumor tissue

- 2.33 Measure serum cytokines and vitamin D at on study and month 6.
- 2.34 Evaluate beta-2 microglobulin plus LDH score as a prognostic factor.
- 2.35 Measure ALC, AMC, and ALC/AMC ratio at on study and after treatment.
- 2.36 Compare quality of life as measured by the FACT-Lym between arms.

3.0 Patient Eligibility

3.1 Inclusion Criteria

- 3.11 Age \geq 18 years.
- 3.12 Histological confirmation of follicular lymphoma grades I, II diagnosed within 12 months (365 days) prior to registration. NOTE: The day of biopsy should be used as Day 1 of diagnosis for this calculation.
- 3.13 Stage I, II, III, or IV disease. NOTE: Stage I disease are eligible only if the disease is not amenable to external beam radiation therapy.
- 3.14 No indication for chemotherapy; candidate for observation.
- 3.15 Measureable disease by tumor imaging with at least one lesion \geq 1.5 cm in at least one dimension.
- 3.16 Previously untreated. NOTE: This includes any chemotherapy or immunotherapy or RIT. Patients who received corticosteroids for diseases other than lymphoma are eligible as long as prednisone dose is \leq 10 mg/day.
- 3.17 Low tumor burden as defined by GELF criteria (2):
 - No tumor mass (nodal or extranodal) \geq 7 cm in one dimension on CT
 - Fewer than 3 (2 or less) nodal masses $>$ 3 cm
 - No systemic or B symptoms
 - No splenomegaly greater than 16 cm by CT scan
 - No risk of organ compression – ureteral, orbital, neurological, gastrointestinal
 - No leukemic phase ($>5.0 \times 10^9/L$ circulating FL cells in the blood as detected by CBC with differential and smear)
 - No cytopenias – ANC $<$ 1000 or platelets $<$ 100,000
- 3.18 Meet standard criteria for RIT:
 - $<25\%$ marrow involvement with FL
 - No evidence of myelodysplasia
- 3.19a ECOG Performance Status (PS) 0, 1, or 2 (Appendix I).

3.19b The following laboratory values obtained \leq 28 days prior to registration:

- Absolute neutrophil count (ANC) \geq 1500/mm³
- Platelet count \geq 100,000/mm³
- Hemoglobin $>$ 10.0 g/dL
- Total bilirubin \leq 1.5 x upper limit of normal (ULN) or if total bilirubin is $>$ 1.5 x ULN, the direct bilirubin must be \leq ULN
- Alkaline phosphatase \leq 3 x ULN
- Aspartate transaminase (AST) \leq 3 x ULN
- Creatinine \leq 2 x ULN

3.19c Negative pregnancy test done \leq 7 days prior to registration, for women of childbearing potential only.

3.19d Provide informed written consent.

3.19e Willing to travel to a radioimmunotherapy site for Zevalin, if necessary.

3.19f Willing to return to the enrolling institution for follow-up (during the Active Monitoring Phase of the study).

*Note: During the **Active Monitoring** Phase of a study (i.e., active treatment and observation), participants must be willing to return to the consenting institution for follow-up.*

3.19g Willing to provide blood samples at baseline for correlative research purposes and tissue for central pathology review (see Sections 6.2, 14.0, and 17.0).

3.19h <25% bone marrow involvement of cellular marrow with lymphoma as determined by bilateral bone marrow aspirate and biopsy. NOTE: The percent involvement should be estimated by the hematopathologist using all of the biopsy material.

3.19i Has insurance coverage or is willing to pay for protocol therapy (rituximab x 4 or Zevalin x 1)

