3.2 Exclusion Criteria

3.21 Any of the following because this study involves an agent whose genotoxic, mutagenic and teratogenic effects on the developing fetus and newborn are unknown:

- Pregnant women
- Nursing women
- Men or women of childbearing potential who are unwilling to employ adequate contraception for at least three months after completing study treatment.

3.22 Co-morbid systemic illnesses or other severe concurrent disease which, in the judgment of the investigator, would make the patient inappropriate for entry into

this study or interfere significantly with the proper assessment of safety and toxicity of the prescribed regimens.

- 3.23 Patients known to be HIV positive and currently receiving antiretroviral therapy.
- 3.24 Uncontrolled intercurrent illness including, but not limited to, ongoing or active infection, symptomatic congestive heart failure, unstable angina pectoris, uncontrolled cardiac arrhythmia, or psychiatric illness/social situations that would limit compliance with study requirements.
- 3.25 Receiving any other investigational agent that would be considered as a treatment for the lymphoma.
- 3.26 Active other malignancy requiring treatment that would interfere with the assessments of response of the lymphoma to protocol treatment and would interfere with follow-up assessments through year 5.
- 3.27 Presence of CNS lymphoma.
- 3.28 Known to have lymphoma related to HIV or AIDS. NOTE: These patients are excluded because it is unknown what effects prolonged B-cell depletion will have on these patient's immune system.
- 3.29a Abnormal renal function (serum creatinine $>2 \times$ ULN).
- 3.29b Received prior external beam radiation therapy for another reason to $>25\%$ of active bone marrow (see form in Appendix IV).
- 3.29c Serious non-malignant disease such as active infection or other condition which in the opinion of the investigator would compromise other protocol objectives.
- 3.29d Major surgery other than diagnostic surgery ≤ 4 weeks prior to registration.
- 3.29e Any evidence of myelodysplastic syndrome or marrow chromosomal changes suggesting myelodysplasia (-7, -5 etc).
- 3.29f Corticosteroid therapy at the time the patient enters the protocol. NOTE: Patients using prednisone or its equivalent for adrenal failure or using ≤ 10 mg of prednisone/day for other benign causes are accepted.
- 3.29g Follicular grades IIIA or IIIB are not eligible.

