4.0 Test Schedule

Tests and procedures	Baseline (Prior to Registration)	Active Monitoring*			
		Cycle 1		Observation	
	≤28 days prior to reg.	Week 5,6, 7 post Zevalin for Arm B pts only	Month 3 post Day 1 of treatment ^{11,12}	Month 6 post Day 1 of treatment ^{11,12}	Months 9, 12, 18, 24, 30, 36, 48, 60 post Day 1 of treatment ^{11,12}
History and exam, weight, PS	X			X	
Height	X				
Tissue confirmation of FL grade I or II from routine diagnostic tissue ≤365 days prior to registration ⁸	X				
Adverse event assessment	X		X	X	
Hematology: WBC, ANC, ALC, AMC, Hgb, PLT	X	X ⁹	X	X	X
Lactate dehydrogenase (LDH) - include ULN	X			X	X
Chemistry: Creatinine, Glucose, SGOT (AST), Alk phos, Ca, T. Bili, uric acid	X			X	
Beta-2 microglobulin (B2M)	X			X	
Direct bilirubin ³	X				X
Serum pregnancy test ¹	X				
Bone marrow biopsy – unilateral or bilateral	X ⁵			X ⁶	
Tumor Measurement/Evaluation of indicator lesion (CT, MRI, etc.) CT Scan chest, abdomen and pelvis or PET/CT; measurements should be by CT or the CT portion of a PET/CT. May use MRI in situations that identify lesion more clearly than CT ²	X			X	X (months 12, 24, 36, 48, 60)
Research tissue ^R	X ⁴				
Research bloods ^{7,R}	X			X	
Hepatitis B and C screen ¹⁰	X				
Quantitative serum immunoglobulins: IgG, IgA, IgM	X ⁵				
QOL (FACT-Lym)	X ¹³		X ¹³	X ¹³	X ¹³

1. For women of childbearing potential only. Must be done ≤7 days prior to registration.
2. Use the same method throughout the study. See Section 11.0 for response criteria.
3. To be done only if the total bilirubin is abnormal.

4. Patients will be requested to submit paraffin embedded tumor for research purposes. This is optional and the patient can participate in the study without providing this sample. Patients at Mayo Clinic will be requested to provide an optional fresh research biopsy.
5. Bone marrow and immunoglobulins acceptable within 180 days prior to registration.
6. Repeat bone marrow only in patients with an initial positive bone marrow
7. Research bloods at baseline (visit 1/screening) and end of six months (visit 2/End of Cycle 2) only. The baseline samples can be collected after the patient consents but prior to starting treatment.
8. Patient can be registered with local pathology review; central review will be done on all cases (see Section 17.0).
9. CBCs should be drawn weekly or until ANC \geq 1000 and platelets \geq 50,000 at physician discretion.

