6.2 Correlative Research

A mandatory correlative research component is part of this study, the patient will be automatically registered onto this component (see Sections 3.19g and 14.0).

An optional correlative research component is part of this study, there will be an option to select if the patient is to be registered onto this component (see Section 17.0).

- Patient has/has not given permission to have additional tissues collected from their diagnostics biopsy submitted for research.
- Patient has/has not given permission to obtain the optional fresh research tissue biopsy prior to starting treatment. **(Mayo patients only)**

6.3 Documentation of IRB approval must be on file in the Registration Office before an investigator may register any patients.

In addition to submitting initial IRB approval documents, ongoing IRB approval documentation must be on file (no less than annually) at the Registration Office [REDACTED]. If the necessary documentation is not submitted in advance of attempting patient registration, the registration will not be accepted and the patient may not be enrolled in the protocol until the situation is resolved.

When the study has been permanently closed to patient enrollment, submission of annual IRB approvals to the Registration Office is no longer necessary.

- 6.4 Prior to accepting the registration, registration application will verify the following:
 - IRB approval at the registering institution
 - Patient eligibility
 - Existence of a signed consent form
 - Existence of a signed authorization for use and disclosure of protected health information
- 6.5 At the time of registration, the following will be recorded:
 - Patient has/not given permission to store and use his/her sample(s) for future research of lymphoma by the Lymphoma SPORE.
 - Patient has/not given permission to store and use his/her sample(s) for future research to learn, prevent, or treat other health problems.
 - Patient has/not given permission for Lymphoma SPORE to give his/her sample(s) to researchers at other institutions.
- 6.6 Treatment cannot begin prior to registration and must begin \leq 21 days after registration.
- 6.7 Pretreatment tests/procedures (see Section 4.0) must be completed within the guidelines specified on the test schedule.
- 6.8 All required baseline symptoms (see Section 10.6) must be documented and graded.

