7.2 Treatment Schedule – Arm B: Zevalin

Agent	Dose	Route	Day	Cycle Length
Rituximab ¹	250 mg/m ² /day	IV	1, 8	3 months
Zevalin	0.3 mCi/kg or 0.4 mCi/kg**	IV	8*	

- * Administer within 4 hours of completion of rituximab infusion.
- ** Maximum dose = 32 mCi. Dose at 0.4 mCi/kg for patients with platelet counts greater than or equal to 150,000/mm³ and at 0.3 mCi/kg for patients with platelet counts 100,000 to 149,000/mm³
- 1. Substitution of a rituximab biosimilar covered by patients' insurance plan is not allowed for Arm B.

The following pre-medications are suggested prior to rituximab: acetaminophen 650-1000 mg PO 30 minutes prior to rituximab and every 4 hours as needed for infusion related reactions (maximum of 4000 mg in 24 hours), diphenhydramine 50 mg PO 30 minutes prior to rituximab, diphenhydramine 25 mg IV every 4 hours as needed for infusion related reactions, meperidine 25 mg IV push as needed for rigors, may repeat x 1 dose if first dose is ineffective.

- 7.3 For this protocol, patients randomized to Zevalin can be treated either at the enrolling site or referred to Mayo Clinic Rochester, Arizona, or Florida for the Day 1, 8 rituximab and Zevalin on Day 8. The enrolling site is also permitted to provide Day 1 rituximab if this is prearranged and coordinated with the Zevalin site. This can be arranged by calling the study [REDACTED] after the patient has been registered.

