4. Patients with preexisting cardiac conditions including arrhythmias and angina have had recurrences of these events during Rituxan therapy and should be monitored throughout the infusion and immediate post-infusion period.
5. It has been found that patients with bulky disease (lesion >10 cm in diameter) have an increased incidence of adverse events. Monitor for signs and symptoms of tumor lysis syndrome, and acute renal failure.
6. An infusion-related symptom complex consisting of fever and chills/rigors occurs in the majority of patients during the first infusion. These reactions generally occur within 30 minutes to 2 hours of beginning the first infusion and resolve with slowing or stopping the infusion and giving supportive care. The incidence of adverse reactions decreased from 80% to 40% with subsequent infusions.
7. Cytopenias are common and can be long term. Monitor CBC. Instruct patient to report signs and symptoms of infection, excessive bruising and/or bleeding to the health care team.
8. GI disturbances (Nausea, abdominal pain and less commonly diarrhea, vomiting, dyspepsia) headache, and weakness are common side effects. Treat as necessary. Monitor for effectiveness.
9. Adequate birth control measures should be used during therapy and for 12 months following therapy. Women should not breastfeed while drug is detectable in serum.
10. Endocrine and metabolic disturbances can be seen (hyper/hypoglycemia, hypocalcemia, hypocholesterolemia, hyperphosphatemia, hyperuricemia). Monitor labs and for signs or symptoms of these conditions. Treat accordingly.
11. There is the possibility of reactivation of Hepatitis B (HBV). Patients who are at high risk of hepatitis B virus should be screened prior to initiation of therapy, carriers of hepatitis B should be closely monitored.

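### The only required pregnancy test is timed to registration, so it can be 35 days old at Zevalin; separately, the contraception floor is shorter than the drug section advises

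*Combined protocol and SAP*

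**What the plan says.** **Testing.** Section 3.19c makes one test an eligibility condition: "Negative pregnancy test done \leq 7 days prior to registration, for women of childbearing potential only". In the test schedule (4.0) the serum pregnancy test has a single entry, and footnote 1 places it before registration: "For women of childbearing potential only. Must be done ≤7 days prior to registration". Section 6.7 says that pretreatment tests "must be completed within the guidelines specified on the test schedule", so the registration section adds no test of its own.

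**Dosing.** Section 6.6 states: "Treatment cannot begin prior to registration and must begin \leq 21 days after registration". Arm A receives rituximab on Days 1, 8, 15 and 22 (7.1). Arm B receives rituximab on Days 1 and 8, with Zevalin within 4 hours of the Day 8 infusion (7.2). Section 7.3 allows referral to a Zevalin site "for the Day 1, 8 rituximab and Zevalin on Day 8", and also allows the enrolling site to give the Day 1 rituximab.

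**Hazard and contraception.** Section 3.21 excludes pregnant women because the study involves an agent whose "genotoxic, mutagenic and teratogenic effects on the developing fetus and newborn are unknown". It also excludes men or women of childbearing potential who are "unwilling to employ adequate contraception for at least three months after completing study treatment". The rituximab nursing guidelines (15.19, item 9) advise: "Adequate birth control measures should be used during therapy and for 12 months following therapy".

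**The concern.** The test is timed to registration, but the fetal hazard named in 3.21 arises when drug is given. Between the two lie up to three weeks before Day 1 and, in Arm B, a further week before the radiolabelled antibody. A pregnancy that began after the registration test, or too early for it to detect, would not be looked for again under the protocol. A site could follow every stated window and still give rituximab, and then Y-90 Zevalin, without a recent check.

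The contraception wording raises a second, separate matter. A patient willing to use contraception for only three months after treatment is eligible under 3.21, although the protocol's own drug section advises 12 months after rituximab.

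Both matters concern participant safety. Neither touches the primary endpoint, the power or any analysis.

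**Working it through.** The plan states no maximum test age at dosing, so there is no figure of its own to reproduce. The check adds up the permitted windows.

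**Inputs**
- Test to registration: a = 0 to 7 days (3.19c; 4.0 footnote 1).
- Registration to Day 1: b = 0 to 21 days (6.6).
- Day 1 to Zevalin: 8 − 1 = 7 days (7.2), assuming Day 8 is given on schedule. The protocol states no window or delay rule for Day 8.

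**Age of the test at each dose**
- First rituximab, both arms: a + b. Lowest 0 + 0 = 0 days; highest 7 + 21 = 28 days.
- Zevalin, Arm B: a + b + 7. Lowest 0 + 0 + 7 = 7 days; highest 7 + 21 + 7 = 35 days.

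For Arm B the age at Zevalin is more than 7 days whenever a + b > 0. It is exactly 7 days only when a = b = 0, that is, when test, registration and Day 1 share a date. This does not depend on the windows being used in full.

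**Effect of a test on Day 1.** A sample drawn on Day 1, with the result known before rituximab, is 0 days old at Day 1 and 8 − 1 = 7 days old at Zevalin.

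**Contraception.** In Arm A the last study drug is the Day 22 rituximab. In Arm B it is Zevalin, given on the same day as the last rituximab. So time after completing treatment and time after rituximab run from the same day in each arm, and the two periods compare directly: 12 − 3 = 9 months. Section 15.15 gives rituximab as detectable in serum for 3 to 6 months after treatment, so the three-month floor can end while drug is still present. The condom advice in 15.29 covers only the week after Zevalin.

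**How many women.** Section 16.83 expects 58 women among 128 patients, so 58 / 2 = 29 per arm at 1:1. The proportion of childbearing potential is not given; for Arm B the possible range is 0 to 29. As a guide only, Section 1.2 reports a median age of 60 in a 50-patient cohort of untreated follicular lymphoma given one course of Zevalin. If women here had that median age, about 58 / 2 = 29 across both arms would be 60 or younger, or about 14 to 15 in Arm B, and those of childbearing potential would be fewer still.

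**The case against.** The strongest reply is that the protocol applies 7 days to registration and to nothing else. Other baseline tests use the same anchor: laboratory values within 28 days and marrow within 180 days before registration. A reader might infer from the 28- and 35-day figures that the plan breaks its own 7-day rule. It does not, because no section sets a test age at dosing. This part of the reply stands in full.

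It is also fair that moving the baseline test to Day 1 does not keep the test recent through Arm A. A test taken 7 days before Day 1 would be 7 + 21 = 28 days old at the Day 22 rituximab, and even a Day 1 sample would be 21 days old. This stands too. The case for a change is therefore firmest for Zevalin, and the Day 1 anchor is a preference.

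There are mitigations. Section 3.21 excludes those unwilling to use contraception, item 9 of 15.19 advises it during therapy, both agents are commercial products, and Section 15 sends users to the package inserts. Sites may retest under local practice, and the consent pages are not available to read. These lower the risk, but willingness to use contraception does not establish pregnancy status before a radiolabelled dose, and no available protocol section requires a retest.

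On contraception, the two statements are not a strict contradiction, since 3.21 sets a minimum. But that minimum admits a patient who intends to stop nine months before the advised period ends.

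**Conclusion.** The point holds as a modest, inexpensive safety improvement. At worst, a compliant negative test is 28 days old at first rituximab and 35 days old at Zevalin. In Arm B it is more than 7 days old at Zevalin in every case but the same-day one. Both maxima assume that each window is used in full and that Zevalin is given on Day 8. The documents give no typical interval, so these figures should not be read as the usual test age.

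Nor do the documents support inferring that pregnant women are likely to be treated. Exposure would require a pregnancy missed by, or begun after, the negative test, despite agreed contraception, in what is probably a small group. No endpoint, sample size or analysis is affected.

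The contraception mismatch is a separate finding: a floor of three months against advice of 12, in a trial where both arms receive rituximab.

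**What to change.** 1. In 3.19c and footnote 1 of 4.0, require for women of childbearing potential in Arm B a negative serum test within 7 days before Zevalin. A sample drawn on Day 1, with the result known before rituximab, meets this. Repeat it if Zevalin is delayed past Day 8. Where the enrolling site gives Day 1 rituximab under 7.3, it should send the result to the Zevalin site.
2. Preferably, also require the baseline test to fall within 7 days before Day 1 in both arms. The registration test stands if it falls in that window.
3. Separately, change the contraception period in 3.21 to 12 months after completing study treatment, in line with 15.19 item 9.

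**Cost.** In Arm B, about one extra blood test per woman of childbearing potential, and a second if Zevalin is delayed. In Arm A, none under item 1 and at most one under item 2. A Day 1 sample uses an existing infusion visit, but the infusion must wait for the result. Item 3 lengthens the commitment by 9 months, which the drug section already advises. As 3.21 is worded, this would apply to men as well as women, and item 9 does not distinguish between them.
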